Testing the Impact of Two Posters on Contraceptive Knowledge, Contraceptive Preferences, and Perceived Pregnancy Risk

NCT number NCT03372369

Document Date December 22, 2017

Primary Investigator [name] PhD

Co-Primary Investigator [name] [name]

Co-Investigators [name]; [name];

[name]; [name]

[name], PhD

Study Design

We survey women before and after random administration of one of two educational posters informing readers about contraception. Baseline data for both groups will be collected on our three outcomes: contraceptive knowledge, willingness to use effective contraception, and perceived pregnancy risk. Participants will then be randomly shown one of the two fact sheets. Then post-exposure questions on the three outcomes will be asked.

Comparators

Shown in Figures 1 and 2 are the two posters that will be tested in this clinical trial.

[figure not shown]
Procedures

We will use Amazon Mechanical Turk to recruit participants.

The survey will first be tested with N=20 participants using the procedures described below. This will be done to estimate the length of time necessary to complete the survey so that accurate time estimates can be provided to potential participants. This will also enable the researchers to ensure that any technical problems with the survey are corrected before the main research data is collected. Data collected in this phase will not be analyzed unless no changes are made to the study materials after reviewing the data.

Once the survey procedures are tested, we will recruit approximately N=1000 participants to complete the survey (final N=990).

Figure 1: CDC Contraceptive Poster

CS 242797

U.S. Department of
Health and Human Services
Centers for Disease
Control and Prevention

CONDOMS SHOULD ALWAYS BE USED TO REDUCE THE RISK OF SEXUALLY TRANSMITTED INFECTIONS.

Other Methods of Contraception

[figure not shown]
Lactational Amenorrhea Method: LAM is a highly effective, temporary method of contraception.

Emergency Contraception: Emergency contraceptive pills or a copper IUD after unprotected

intercourse substantially reduces risk of pregnancy.

Adapted from World Health Organization (WHO) Department of Reproductive Health and Research, Johns Hopkins Bloomberg School of Public Health/Center for Communication Programs (CCP), Knowledge for health project, Family planning: a global handbook for providers (2011 update), Baltimore, MD; Geneva, Switzerland: CCP and WHO; 2011; and Trussell J. Contraceptive failure in the United States. Contraception 2011;83:397-404.

Figure 2: New Contraceptive Poster

The study uses an online survey. Subjects will be recruited through Amazon Mechanical Turk's website. Amazon Mechanical Turk is an online service, which allows individuals to post surveys to be completed for a small amount of money. The job posting will include a very general description of the study, but no indications about the eligibility criteria. If a person is interested in participating, they will click on a link, which will take them to a short screening Qualtrics survey. If the person is eligible based on the screening survey, they will be given permission to view and complete the full survey. Data from the screening survey will not be downloaded or kept. The full survey will also be posted on Amazon Mechanical Turk, with the same general description of the study methods. If an eligible person is interested in completing the full survey, they will click on the link in the posting, which will take them to the full Qualtrics survey. There they will see the informed consent information and will be required to give their informed consent before they participate in the survey. We expect that the survey will take 30 minutes, on average, to complete.

After completing the survey, the survey will show the participant a unique code that they can enter into the Amazon Mechanical Turk form. This will be used to ensure that study participants are compensated for completing the survey. This code will not be recorded in our data set. Study compensation \$0.05 for the screening survey and \$3.60 for the full survey. This is approximately equivalent to the federal minimum hourly wage, which should be a reasonable but not coercive incentive for participants.

The study was approved by the University of North Carolina at Chapel Hill Institutional Review Board (IRB number 17-2955).

Measures

This study measured change in the mean scores for three primary outcomes: contraceptive knowledge, effectiveness of most likely contraceptive method used in the next year, and accuracy of perceived pregnancy risk. We gathered baseline and follow-up measures for each of these outcomes immediately before and after the intervention, respectively.

Contraceptive knowledge was measured objectively using the 25-item Contraceptive Knowledge Assessment.¹ This produced a score between 0 (0% correct) and 25 (100% correct). Our contraceptive knowledge outcome was the change in this score between baseline and follow-up.

Effectiveness of most likely contraceptive method was operationalized using a woman's intention to continue using her current contraceptive method and the contraceptive method she reported being most likely to switch to were she to change methods in the next year. This measure was intended to be a realistic measure of the contraceptive method that women were most likely to use in the next year. We first asked women at both baseline and follow-up: "Do you intend to use the same birth control method(s) that you are currently using for the next year?" If the woman said she intended to keep her contraceptive method(s), the effectiveness of the most effective method she used in the past three months was used as her most likely method of contraception. The effectiveness of contraceptive methods was scored using the following WHO-defined categories²: IUDs, implants, and sterilization were considered highly effective (score = 3, 0-1% annual failure rate); the pill, patch, ring, and injection were considered effective (2, 2-9% annual failure rate); condoms, withdrawal, fertility tracking, and other methods were considered less effective (1, 10-30% annual failure rate); and no method

was its own category (0, 85% annual failure rate). If a woman said she did not intend to keep her current contraceptive method, we used the effectiveness of the most likely alternative contraceptive she would use. We measured this with the question, “If you had to change to a new birth control method in the next year, which of the following methods would you consider using?” Participants selected each method they would consider and then ranked the selected methods from most to least likely method. Our “effectiveness of most likely contraceptive method” outcome was the difference between a woman’s score at baseline and follow-up.

Finally, accuracy of perceived pregnancy risk was assessed by comparing a woman’s current contraceptive method to her perceived pregnancy risk. Perceived pregnancy risk was measured using the following question: “What is your chance of getting pregnant this year?” with possible responses being very high (score = 5, annual pregnancy risk >50%), high (4, annual pregnancy risk 25-50%), moderate (3, annual pregnancy risk 5-25%), low (2, annual pregnancy risk 1-5%), and very low (1, annual pregnancy risk ≤1%). We assessed the accuracy of perceived risk based on the most effective birth control method a woman used in the past three months. In accordance with the WHO categories², for highly effective methods, we coded an accurate perception to be very low risk; for effective methods, an accurate perception was low or moderate risk; for less effective methods, an accurate perception was moderate or high risk; for no method, an accurate perception was very high risk. An accurate perception was assigned a score of 1 and an inaccurate perception, 0. Our accuracy in perceived pregnancy risk outcome was the change in this score between baseline and follow-up.

Baseline data were collected on factors that might influence these outcomes. We measured prospective pregnancy intentions with the question, “Are you currently trying to get

pregnant or avoid pregnancy?”³ We measured past pregnancy scares by asking: “Have you ever had a pregnancy scare; that is, thought you were pregnant when you didn’t want to be, but later discovered that you weren’t pregnant after all?” We measured numeracy using the Berlin single item numeracy scale.⁴ This scale has been tested and validated to show that people who answer this question correctly are in the top 50% of the population in numeracy.⁴ Data were also collected on the sexes of the woman’s past sex partners, whether she had ever seen the poster before, and whether there were any types of birth control the woman could not use for health/safety or cost reasons. The following variables were measured using questions from the National Survey of Family Growth (NSFG): biological sex, age, whether the participant was trying to conceive or was currently pregnant, sexual intercourse in the past three months, education, time since first sex, and marital status. Finally, the following variables were measured using questions from the National Longitudinal Survey of Adolescent to Adult Health (Add Health): race/ethnicity (Wave V), income (Wave IV), relationship status (Wave IV), and health insurance type (Wave IV).

Analysis

We first tested whether the demographic and other factors were balanced between our randomized groups using two-sample t-tests and likelihood-ratio tests as appropriate. We did not find any statistically significant imbalances for any of the variables. We conducted two-sample t-tests on the change in the mean score for each of our outcomes to test whether each poster improved the three primary outcomes relative to baseline and in comparison to the other poster. We used the Bonferroni correction to account for multiple comparisons. Using the

same methods, we also tested the hypothesis that the three pre-specified subgroups (low numeracy, pregnancy scares, and no birth control) had greater increases in their mean scores for the patient-centered poster versus the CDC poster. We chose these subgroups because the patient-centered poster was designed to appeal to the needs of these groups. Finally, because correct answers to some of the questions on the Contraceptive Knowledge Assessment were not given by either poster, we could determine the proportion of the change in contraceptive knowledge that was attributable to the posters. We did this by analyzing the change in contraceptive knowledge separately for questions that did and did not have the correct answer provided by either poster. All analyses were conducted in Stata (Stata/SE 15, College Station, TX, US).

For our power calculations, we assumed an alpha of 1% and a power of 80%. For our final analysis sample of N=936, comparing the two posters we can detect a 3 percentage point difference in mean change in contraceptive knowledge (standard deviation of 0.18¹), a 0.8 percentage point difference in accuracy of perceived pregnancy risk (standard deviation of 0.05), and a 6 percentage point difference in the mean change in effectiveness of most likely contraceptive method (standard deviation of 0.35⁵).

References

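### The intention question asks about the current method, but a *yes* is scored on the best method of the past three months, so women who stepped down and then change their answer get a wrong change score

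*Combined protocol and SAP*

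**What the plan says.** The Measures section of the combined protocol and SAP builds this primary outcome from an intention question and a scoring rule with two branches.

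- The question, put at baseline and at follow-up: "Do you intend to use the same birth control method(s) that you are currently using for the next year".
- If she answers *yes*: "the effectiveness of the most effective method she used in the past three months was used as her most likely method of contraception".
- Otherwise: "If a woman said she did not intend to keep her current contraceptive method, we used the effectiveness of the most likely alternative contraceptive", which is the top-ranked method among those she would consider.

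The scale has four categories: 3 for an IUD, an implant or sterilization (yearly failure 0–1%); 2 for other hormonal methods such as the pill or ring (2–9%); 1 for condoms and all remaining methods (10–30%); and 0 for using nothing (85%).

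The outcome is the difference between the two scores. On timing: "We gathered baseline and follow-up measures for each of these outcomes immediately before and after the intervention, respectively". The method in use therefore cannot change between the two measurements; only the stated intention can.

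The perceived-risk outcome in the same section also takes the best method of the past three months as the current one. The document describes no separate item on the method in use now, no rule for women who stopped or stepped down within the window, and no alternative scoring.

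**The concern.** The question and the score for a *yes* refer to different periods. They agree only when the woman's best category in three months is also her category now. If her category fell within the window, a *yes* commits her to the lower category but is scored on the higher one. Because the rule takes a maximum over the window, it can only over-score a *yes*; women who stepped up or stayed in the same category are scored correctly.

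The *no* branch has no such error, because it uses the method she names. The excess therefore does not cancel in the change score when her answer differs before and after the poster. This is a primary outcome. The Analysis section tests it both within each poster group against baseline and between the posters. A woman who moves to a better method can be recorded as unchanged or worse.

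**Working it through.** **Inputs.** From Measures: the 0–3 scale and the two-branch rule. Let *c* be the category in use now, *m* the highest category in the past three months, and *f* the category of the top-ranked alternative. An error needs *m* > *c*. The actual change below means the change when a *yes* is scored on *c*.

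**The plan's own figure.** The plan gives no figure for how many women have *m* > *c*. Its only numbers for this outcome are in the power paragraph under Analysis: a detectable difference of 6 percentage points, SD 0.35, N = 936, alpha 1%, power 80%. With equal arms of 468 and a two-sided test (both assumed), 0.35 × (2.576 + 0.842) × √(2/468) = 0.078, not 0.06. That mismatch is a separate matter, and nothing below uses the figure.

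**Error by answer pattern, for a woman with *m* > *c*.**

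| Before → after | Recorded | Actual | Error |
|---|---|---|---|
| yes → yes | m − m = 0 | c − c = 0 | 0 |
| no → no | f₂ − f₁ | f₂ − f₁ | 0 |
| yes → no | f − m | f − c | −(m − c) |
| no → yes | m − f | c − f | +(m − c) |

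**Examples.**
- IUD removed, condoms now (m = 3, c = 1), *yes* then *no* with the pill (f = 2): recorded 2 − 3 = −1, actual 2 − 1 = +1.
- Pill earlier, condoms now (m = 2, c = 1), *yes* then *no* with an IUD (f = 3): recorded 3 − 2 = +1, actual 3 − 1 = +2.
- The first woman in the opposite order, *no* with the pill and then *yes*: recorded 3 − 2 = +1, actual 1 − 2 = −1.

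**All yes → no cases.** There are six (c, m) pairs with m > c and four values of f, so 6 × 4 = 24 combinations:
- a gain recorded as a loss (c < f < m): 4, namely (c, m, f) = (0,2,1), (0,3,1), (0,3,2), (1,3,2);
- a gain recorded as zero (f = m): 6;
- no change recorded as a loss (f = c): 6;
- sign kept but change too low by m − c: 8.

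These are counts of scoring patterns, not probabilities. The document does not say how a woman using nothing answers the question. Leaving out c = 0 gives 12 combinations, with 1, 3, 3 and 5 in the same four groups.

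**Size, under assumptions.** Let *p* be the share of an arm that answers *yes* at baseline with m > c, *q* the share of those who switch to *no*, and *e* = m − c. The arm mean shifts by −p·q·e, before any offset from women going from *no* to *yes*.
- Low: 0.02 × 0.10 × 1 = 0.002. High: 0.10 × 0.30 × 2 = 0.06.
- In women per arm of 468: 0.02 × 0.10 × 468 ≈ 1 to 0.10 × 0.30 × 468 ≈ 14 who switch.

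The contrast shifts by −p·e·(q_A − q_B). With q differing by 0.10, this is 0.02 × 1 × 0.10 = 0.002 to 0.10 × 2 × 0.10 = 0.02, against the poster that moves more of these women to *no*.

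**The case against.** A three-month window is a reasonable and consistent proxy for current use, since the perceived-risk outcome uses it too. It suits condoms, withdrawal and fertility tracking, where use now is hard to define. Scoring strictly on the day of the survey could code an intermittent condom user as 0. This stands, and it shapes the fix. But it defends the window, not its pairing with a question about a different period.

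The error also needs several things at once: a fall in category within three months, a *yes* at one measurement, and a different answer at the other within one sitting. That may be uncommon, and the documents cannot settle it. A woman using nothing may answer *no*, in which case her baseline score has no error.

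Randomisation balances, on average, who has m > c. That helps the between-poster comparison but not the within-group tests against baseline. Nor does it guarantee cancellation between posters, because the error enters through changed answers, which the poster can influence.

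A reader might infer that every woman who stopped or stepped down gets a wrong starting score. The rule does not do that: a baseline *no* is scored on the alternative, and a move within a category (pill to ring) changes nothing. A reader might also suppose that recent stoppers are especially responsive to a poster; the documents give no basis for this.

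**Conclusion.** The mismatch is in the current text and nothing elsewhere corrects it. Followed exactly, the rule gives a wrong change score to women whose category fell within three months and whose answer differs before and after the poster. The change is too low for *yes* to *no* and too high for *no* to *yes*. Full sign reversal is the narrow case: a drop of at least two categories with the chosen method strictly in between.

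The size is unknown. The ranges of 0.002–0.06 score points for an arm mean and 0.002–0.02 for the contrast rest wholly on the assumed p, q and e, and on a 10-point difference in switching for the contrast.

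A reader might note that 14 women at 2 points in an arm of 468 make 0.06 and conclude that the error can equal the plan's detectable difference. The documents do not support that. The 6 percentage points are a between-poster difference, so there would have to be 14 more such women in one arm than in the other. The units are also unclear. The power paragraph states knowledge, scored 0–25, in percentage points with SD 0.18, which suggests rescaling to 0–1; on that reading 6 points is 0.06 × 3 = 0.18 score points. The point is a cheap measurement improvement, not evidence that the comparison is invalid.

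**What to change.** Make the question and the score refer to the same method, in one of two ways:

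- add a baseline item on the method(s) she currently uses when she has sex, with *none* as an option, and score a *yes* on the most effective of those; or
- show in the intention question the three-month method that will be scored, so that a *yes* means keeping that method.

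Keep the three-month scoring as a sensitivity analysis. The cost is one item or one rewording and a small change to the scoring code. Some ambiguity about current use remains for intermittent methods.

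The document mixes future and past tense, and its Analysis section already reports balance results, so the survey may be closed. In that case, re-score with any current-method item that was collected and report both versions. If there is none, report the mismatch as a limitation of this outcome.

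### Should perceived pregnancy risk for the year be scored against the method a woman newly intends to use, rather than the one she used in the past three months?

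*Combined protocol and SAP*

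**What the plan says.** The Measures section describes the accuracy outcome as a comparison of a woman's "current contraceptive method to her perceived pregnancy risk". The question put to her is "What is your chance of getting pregnant this year", with five answers from very low (at most 1% a year) to very high (above 50%). The reference is recent use: "We assessed the accuracy of perceived risk based on the most effective birth control method a woman used in the past three months". Each effectiveness tier has its accepted answers. For women using nothing there is only one: "for no method, an accurate perception was very high risk". A matching answer scores 1, any other scores 0, and the outcome is the change from baseline to follow-up. Follow-up comes immediately after the poster.

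The same section defines another primary outcome, the effectiveness tier of the method most likely to be used in the coming year. It depends on whether the woman intends to keep her method and, if not, on her ranked answers to "If you had to change to a new birth control method in the next year, which of the following methods would you consider using". Using no method "was its own category (0, 85% annual failure rate"). That intended method does not enter the accuracy score, and no start date for a switch is among the measures described. The Analysis section compares each poster with baseline and with the other poster. It also tests whether "three pre-specified subgroups (low numeracy, pregnancy scares, and no birth control) had greater increases in their mean scores" with the new poster.

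**The concern.** The question looks forward over a year, while the reference looks back three months. A poster that works may lead a woman to plan a more effective method and to lower her stated risk accordingly. She then gains on effectiveness and may lose on accuracy, although her answer could be reasonable for the year. Every upward move open to a non-user is exposed to this, and non-users are one of the named subgroups. If one poster prompts more new plans than the other, part of any difference in accuracy could reflect intentions rather than judgement of risk. A reader could then take a null or adverse result as poor understanding. The documents do not discuss this.

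**Working it through.** **1. Overlap of accepted answers (Measures section).** Code the answers 1 = very low to 5 = very high. Accepted answers are: tier 3 (highly effective) {1}; tier 2 (effective) {2, 3}; tier 1 (less effective) {3, 4}; tier 0 (no method) {5}.

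| Upward move | Answers accepted for new tier | Score against old tier |
|---|---|---|
| 0 to 1 | 3, 4 | 0, 0 |
| 0 to 2 | 2, 3 | 0, 0 |
| 0 to 3 | 1 | 0 |
| 1 to 2 | 2, 3 | 0, 1 |
| 1 to 3 | 1 | 0 |
| 2 to 3 | 1 | 0 |

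Five of six moves share no accepted answer, and 8 of the 9 answer cells score 0. These are cells, not women; the documents give no frequencies.

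**2. Is the 0 wrong?** Take a non-user who starts a method with annual failure rate f on day d. Using the plan's failure rates and assuming a constant hazard, her risk over the year is

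1 - 0.15^(d/365) × (1 - f)^((365 - d)/365).

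| New tier (f) | An answer accepted for the new tier is true up to | Very high is true after |
|---|---|---|
| 1 (10% to 30%) | 119.7 to 79.7 days (risk at most 50%) | 119.7 to 79.7 days |
| 2 (2% to 9%) | 52.0 to 39.2 days (risk at most 25%) | 130.9 to 121.2 days |
| 3 (0% to 1%) | 1.9 to 0 days (risk at most 1%) | 133.4 to 132.1 days |

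For tier 3 at f = 0, starting after one month already gives 14.6%, and after three months 37.8%. A non-user who plans a tier 3 method and answers very low is thus right only if she starts almost at once; otherwise her 0 is correct. For tiers 2 and 3 there is also an interval in which neither the old-tier nor the new-tier answer is true. Without a start date, neither reference can be called the right one.

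**3. Direction and size.** Let e be the excess share of new switchers in one arm and r the share of them who revise their answer to the new tier. Assume that r is equal by arm, that moves are between tiers with no overlap, and that the rest keep the old-tier answer. If the new tier is the truth for the year, scoring against the past method wrongly gives 0 to revisers (-e × r) and wrongly gives 1 to the others (+e × (1 - r)). The net error is e × (1 - 2r):

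- e = 3%, r = 50%: -1.5 + 1.5 = 0 points.
- e = 3%, r = 25%: -0.75 + 2.25 = +1.5 points.
- e = 6%, r = 25%: -1.5 + 4.5 = +3 points.
- e = 6%, r = 75%: -4.5 + 1.5 = -3 points.

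If the old tier is the truth (late starts), scoring against the past method makes no error by this route. All values of e and r are assumed.

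**4. Against the power statement.** The plan quotes "a 0.8 percentage point difference in accuracy of perceived pregnancy risk (standard deviation of 0.05"). With 468 per arm (equal split assumed), two-sided alpha 1% and power 80%, the two-sample formula gives 3.417 × 0.05 × √(2/468) = 0.0112, or 1.12 points. The stated 0.8 is not reproduced; that is a separate matter and nothing here depends on it. If instead 10-30% of women change score (assumed), the SD is √0.10 = 0.316 to √0.30 = 0.548, the SE is 2.07 to 3.58 points, and the detectable difference is 7.1 to 12.2 points.

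Suppose there is no true difference and a full, un-offset shift of -1.5 points. The chance of a significant adverse result is then Φ(-2.576 + 1.5/2.07) = 3.2% to Φ(-2.576 + 1.5/3.58) = 1.6%, against a nominal 0.5%. That is small, and it leaves out the offset in step 3.

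**The case for a change.** The strongest case for acting is that accuracy is a primary outcome, that declaring a comparator does not tell the reader what the score means over a different period, and that randomisation does not remove the problem. Method intention is itself tested between posters, so equal intentions by arm cannot be presumed, and the comparison with baseline has no other arm to cancel against. A limitation sentence and an untested table would cost little.

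The description stands: the time frames differ, the tiers mostly do not overlap, and no measure described would settle individual cases. What does not stand is a one-directional bias. Counting only revisers gives a downward shift; women who plan to switch and keep their old answer push the other way, in the comparison with baseline as well as between posters. A table showing only new-tier answers would repeat that one-sided reading. Two stronger claims also go too far: that such women will usually score 0, since answer cells are not frequencies, and that no start date was collected, since the documents do not contain the full questionnaire.

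**Conclusion.** No change to the plan. This is a fair trade-off in an openly stated definition. The reference is the method actually used and is in effect the same before and after the poster, so the change score moves only with the woman's answer. The alternative, scoring against the most likely method at each time point, rests on a hypothetical intention, lets the reference move with the intervention, and can penalise the more persuasive poster too: women who keep an old answer that is true because they start late would then score 0.

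The size and sign of any effect on the poster comparison cannot be derived from the documents. Under the assumed rates the net error lies between -3 and +3 points if the new tier is the truth, and is zero by this route if the old tier is. The day windows rest on a constant hazard and the plan's failure rates. The primary scoring, tests and inference would stay as they are in either case. Authors may note in the discussion that accuracy is relative to recent use and that an answer given for a newly intended method may score 0; that is a matter of reporting, and no result depends on it.

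### The change-score t-test between posters is valid but leaves some precision unused, because follow-up is not regressed on the baseline score; the test of each poster against baseline should be named as paired

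*Combined protocol and SAP*

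**What the plan says.** - **Study Design.** "Baseline data for both groups will be collected on our three outcomes", and "Participants will then be randomly shown one of the two fact sheets". No allocation ratio is given.
- **Measures.** Each outcome is a within-woman change. For knowledge: "Our contraceptive knowledge outcome was the change in this score between baseline and follow-up". Effectiveness is treated the same way on a 0 to 3 score, and accuracy of perceived risk on a 0/1 score. For a woman who intends to keep her method, "the effectiveness of the most effective method she used in the past three months was used as her most likely method of contraception".
- **Analysis, tests.** "We conducted two-sample t-tests on the change in the mean score for each of our outcomes to test whether each poster improved" the outcomes "relative to baseline and in comparison to the other poster". One named test thus covers two comparisons: each poster against its own baseline, and poster against poster.
- **Analysis, subgroups.** The text reuses the "same methods, we also tested the hypothesis that the three pre-specified subgroups" gained more from one poster than from the other.
- **Analysis, power.** With N=936, alpha 1% and power 80%, "comparing the two posters we can detect a 3 percentage point difference in mean change in contraceptive knowledge" (SD 0.18). The other planning SDs are 0.05 for accuracy and 0.35 for effectiveness.

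No regression, ANCOVA or covariate adjustment is named. Each baseline score enters its analysis by subtraction only.

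**The concern.** Subtracting the baseline is one particular adjustment: it sets the slope of follow-up on baseline to exactly 1. Estimating that slope instead uses data already in hand, estimates the same between-poster effect, and usually gives a narrower interval. The plan works at a strict alpha with a Bonferroni correction and compares two active posters, so unused precision has a cost.

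The second issue is the name of the test. One poster's change from baseline has a single sample of women, each measured twice, and a two-sample test has no second sample to use. If the pre and post scores were treated as independent groups, the within-poster standard errors would be too large.

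**Working it through.** **Inputs.** From the Analysis section: N=936, alpha 1%, power 80%, and SDs 0.18 / 0.05 / 0.35. Assumed because not stated: 1:1 allocation (468 per arm), a two-sided test, and the pre-post correlation r.

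**1. The plan's own figure.** Detectable difference = (z for alpha + z for power) × SD × sqrt(2/468). For knowledge this is (2.576 + 0.842) × 0.18 × 0.0654 = 0.0402, or 4.02 points against the stated 3. If 0.18 is the SD of a single score, the SD of change is 0.18 × sqrt(2(1−r)). At r = 0.7 that is 0.139, giving 3.11 points, which rounds to 3. The text does not say which reading is meant, so both are carried below. Whether the stated differences are right is a separate matter; the variance ratio for a given r does not depend on it.

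**2. Variance ratio.** With equal variances σ² before and after, the change-score variance is proportional to 2σ²(1−r) and the ANCOVA variance to σ²(1−r²). The ratio is (1+r)/2. The equivalent extra sample is 936 × (2/(1+r) − 1). If the follow-up SD is k times the baseline SD, the ratio is k²(1−r²)/(1+k²−2rk).

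| r (assumed) | Ratio, k=1 | CI narrower | Extra women | Ratio, k=1.1 | Ratio, k=0.9 |
|---|---|---|---|---|---|
| 0.5 | 0.75 | 13% | 312 | 0.82 | 0.67 |
| 0.7 | 0.85 | 8% | 165 | 0.92 | 0.75 |
| 0.8 | 0.90 | 5% | 104 | 0.97 | 0.79 |
| 0.9 | 0.95 | 3% | 49 | 1.00 | 0.81 |

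**3. Power for 3 points on knowledge** (noncentral t, 468 per arm, two-sided 1%, k=1).

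| r | 0.18 = SD of change: change score / ANCOVA | 0.18 = SD of one score: change score / ANCOVA |
|---|---|---|
| 0.5 | 49% / 64% | 49% / 64% |
| 0.7 | 49% / 57% | 76% / 84% |
| 0.8 | 49% / 54% | 93% / 95% |
| 0.9 | 49% / 51% | 99.9% / 99.9% |

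Under the first reading the implied one-score SD is 0.18/sqrt(2(1−r)) = 0.18, 0.23, 0.28 and 0.40 on a 0 to 1 scale, so r = 0.9 is hard to square with it.

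**4. The other two outcomes, if their planning SDs are SDs of change.** Here 1−r = (SD of change)²/(2 × one-score variance).
- Accuracy, baseline accuracy assumed 30% or 50%: 1−r = 0.0025/0.42 = 0.006 or 0.0025/0.50 = 0.005. So r is about 0.994 to 0.995 and the ratio about 0.997, worth 2 to 3 women.
- Effectiveness, one-score SD assumed 0.8 or 1.0 on the 0 to 3 scale: 1−r = 0.1225/1.28 = 0.096 or 0.1225/2 = 0.061. So r is about 0.90 or 0.94 and the ratio about 0.95 or 0.97, worth 47 or 30 women.
- The scoring rule for effectiveness also pushes r up, since a woman who intends to keep her method at both surveys scores the same twice. If a share q do so and the rest are uncorrelated with the same score distribution, r = q, and the ratio is 0.85 at q = 70% and 0.95 at q = 90%. The documents do not give q.

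**5. Validity.** In 10,000 simulated trials per setting with no effect, rejection at nominal 1% was 1.03% and 1.06% for the change score (r = 0.5 and 0.8) and 0.93% and 1.17% for ANCOVA.

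**6. Allocation.** The guarantee of no larger variance needs 1:1 allocation or equal baseline slopes. As an example, take 3:1 with slope 0.65 in the larger arm and 0.95 in the smaller. A common-slope model has 1.03 times the change-score variance; adding a poster-by-centred-baseline term brings this to 0.94.

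**7. Each poster against baseline.** With n women and equal variances, the paired SE is σ × sqrt(2(1−r)/n) and the unpaired SE is σ × sqrt(2/n). The unpaired SE is therefore 1/sqrt(1−r) times the paired one: 1.41 at r = 0.5 and 2.24 at r = 0.8.

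**The case against.** The strongest reply is that nothing is wrong. The outcomes are defined as changes, the test compares those changes between randomised groups, and method and definition agree. The size of any gain rests on an r that the documents do not supply. Measurement immediately before and after the poster makes a high r plausible, and the largest figures come from r = 0.5. The analysis is written in the past tense, so an adjusted model may be supportive only.

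Most of this stands, and it limits the point without removing it. It also rules out four stronger readings that a reader might infer:
- *The planned comparison is biased, or ignores the baseline.* It does neither. Randomisation makes it unbiased, and the baseline enters with coefficient 1.
- *Power would rise by 15 points.* That holds for knowledge at an assumed r = 0.5, and the documents do not establish that value.
- *The subgroups would gain most.* The relative gain depends on r and k, not on sample size, and the documents give neither for any subgroup.
- *An unpaired test was run against baseline.* The sentence speaks of tests on change and Measures defines within-woman changes, so a loose label is the natural reading. The text cannot settle it.

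**Conclusion.** The point holds as one of efficiency, not validity; no result is shown to be wrong. With equal variances and 1:1 allocation, baseline adjustment would leave 75% to 95% of the change-score variance for r between 0.5 and 0.9. That is an assumed range, and it is most relevant to knowledge. If the SDs of 0.05 and 0.35 are SDs of change, the gain is close to zero for accuracy (assuming 30% to 50% baseline accuracy) and about 3% to 5% of variance for effectiveness (assuming a one-score SD of 0.8 to 1.0).

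The mismatch between a two-sample test and a within-woman comparison is real. It is only a matter of wording if the changes were tested in one sample, and it affects the within-poster standard errors if they were not.

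**What to change.** - For each outcome, report a linear regression of follow-up score on poster and baseline score, with robust SEs and a CI, beside the planned t-test. For accuracy, the linear form gives a risk difference and so keeps the same effect measure.
- State the allocation ratio. If it is not 1:1, add a poster-by-centred-baseline term.
- Report r for each outcome so that readers can judge the gain.
- Keep the planned t-test as the basis for the main conclusions. Label the regression post hoc if it is added after the data were seen. Repeating it in all three subgroups would bring the total to 3 × 4 = 12 adjusted estimates, so any such extension should be presented as exploratory.
- State that each poster is tested against baseline with a paired t-test (one-sample on within-woman change). If an unpaired test was run, redo it.

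The cost is a few lines of Stata and one corrected sentence, with no new data. If r proves high, the adjusted and planned intervals will be nearly the same.
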